8.3.5 ADVERSE EVENT REPORTING

AEs documented during the course of the trial will be reported to NCCIH on an annual basis by way of inclusion in the annual report and in the annual AE summary which will be provided to NCCIH and to the Independent Monitors. The Independent Safety Monitor(s) Report will state that all AEs have been reviewed.

8.3.6 SERIOUS ADVERSE EVENT REPORTING

Protocol PAR-18-829

SAEs that are unanticipated, serious, and possibly related to the study intervention will be reported to the Independent Monitors(s), IRB, FDA, and NCCIH in accordance with requirements. For the IND:

- 7-day IND Safety Report (unexpected fatal or life-threatening AEs related to the intervention); a copy of the report sent to the FDA will be submitted to the NCCIH Program Officer and Independent Safety Monitor(s) within 24 hours of FDA notification.
- 15-day IND Safety Report (any other serious and unexpected AE related to the intervention); a copy of the report submitted to the FDA will be submitted to the NCCIH Program Officer and Independent Safety Monitor(s) within 24 hours of FDA notification.

All other AEs documented during the course of the trial will be reported to NCCIH on an annual basis by way of inclusion in the annual report and in the annual AE summary which will be provided to NCCIH and to the Independent Monitors. The Independent Safety Monitor(s) Report will state that all AEs have been reviewed

8.3.7 REPORTING EVENTS TO PARTICIPANTS

In the case of abnormal lab values (liver functions), the PI will address these findings with the study subjects and provide the subject with a copy of the result for their current physician.

8.3.8 EVENTS OF SPECIAL INTEREST

None

8.3.9 REPORTING OF PREGNANCY

All individuals of child bearing age range will be required to provide a urine sample for pregnancy testing at the screening PK visit. If they are determined to be pregnant they will be excluded from the study. The pharmacokinetics phase of the study is a one day visit.

8.4 UNANTICIPATED PROBLEMS

8.4.1 DEFINITION OF UNANTICIPATED PROBLEMS (UP)

The Office for Human Research Protections (OHRP) considers unanticipated problems involving risks to subjects or others to include, in general, any incident, experience, or outcome that meets **all** of the following criteria:

- Unexpected in terms of nature, severity, or frequency given (a) the research procedures that are described in the protocol-related documents, such as the IRB-approved research protocol and informed consent document; and (b) the characteristics of the subject population being studied;
- Related or possibly related to participation in the research ("possibly related" means there is a reasonable
 possibility that the incident, experience, or outcome may have been caused by the procedures involved in
 the research); and

• Suggests that the research places subjects or others at a greater risk of harm (including physical, psychological, economic, or social harm) than was previously known or recognized.

8.4.2 UNANTICIPATED PROBLEM REPORTING

Protocol PAR-18-829

Incidents or events that meet the OHRP criteria for unanticipated problems require the creation and completion of an unanticipated problem report form. OHRP recommends that investigators include the following information when reporting an adverse event, or any other incident, experience, or outcome as an unanticipated problem to the IRB:

- Appropriate identifying information for the research protocol, such as the title, investigator's name, and the IRB project number;
- A detailed description of the adverse event, incident, experience, or outcome;
- An explanation of the basis for determining that the adverse event, incident, experience, or outcome represents an unanticipated problem;
- A description of any changes to the protocol or other corrective actions that have been taken or are proposed in response to the unanticipated problem.

To satisfy the requirement for prompt reporting, unanticipated problems will be reported using the following timeline:

- Unanticipated problems that are serious adverse events will be reported to the IRB, Independent Safety Monitor(s), and NCCIH within 7 days of the investigator becoming aware of the event.
- Any other unanticipated problem will be reported to the IRB, Independent Safety Monitor(s), and NCCIH within 14 days of the investigator becoming aware of the problem.

All unanticipated problems should be reported to appropriate institutional officials (as required by an institution's written reporting procedures), the supporting agency head (or designee), and OHRP within one month of the IRB's receipt of the report of the problem from the investigator.

8.4.3 REPORTING UNANTICIPATED PROBLEMS TO PARTICIPANTS

During this study we will follow the NIH and UF IRB guidelines on reporting unanticipated problems to study participants.

9 STATISTICAL CONSIDERATIONS

9.1 STATISTICAL HYPOTHESES

Primary Efficacy Endpoint(s):

Not applicable as this is not an efficacy study.

Secondary Efficacy Endpoint(s):

N/A

9.2 SAMPLE SIZE DETERMINATION

We will recruit and screen potential participants until we are able to randomize 10 healthy individuals into the pharmacokinetics phase of this study. As kava pharmacokinetics have never been characterized in humans, this is a pilot study such that, with 10 participants, these results will provide preliminary data of kava pharmacokinetics in humans. The data will be the foundation for future systematic characterization of kava pk in humans.

9.3 POPULATIONS FOR ANALYSES

Healthy adults ages 18-50

9.4 STATISTICAL ANALYSES

9.4.1 GENERAL APPROACH

Plasma concentration-time data of individual kava lactone in will be subjected to non-linear mixed effect modeling (NONMEM). Compartmental modeling approach will be applied to achieve the best fit model on the basis of residual sum of squared error, Akaike's Information Criterion and objective function value. Chi-squared distribution will be assessed to evaluate the significance; e.g. an objective function change (OBJ) of 3.84 is significant at alpha=0.05.

9.4.2 ANALYSIS OF THE PRIMARY EFFICACY ENDPOINT(S)

Pharmacokinetic parameters will be derived from this study and these parameters will be used to design future efficacy studies

9.4.3 ANALYSIS OF THE SECONDARY ENDPOINT(S)

Not applicable

9.4.4 SAFETY ANALYSES

Protocol PAR-18-829

At several time points in the study we will be collecting blood to access the study subjects liver functions pre and post kava ingestion. In the event that serum liver enzymes become elevated, (e.g., greater than 3 times the upper limits or normal for two repeated measures, or greater than 5 times the upper limits of normal once) the medical monitor will be notified and results will be communicated with the subject along with recommendations for follow up by a hepatologist.

9.4.5 BASELINE DESCRIPTIVE STATISTICS

Gender, age, percentage of subjects on oral contraceptive, percentage of subjects who take multi vitamins.

9.4.6 PLANNED INTERIM ANALYSES

Not applicable

9.4.7 SUB-GROUP ANALYSES

None

9.4.8 TABULATION OF INDIVIDUAL PARTICIPANT DATA

Plasma concentration-time of all the volunteers will be tabulated in a csv file to do pharmacokinetic modeling and simulation.

9.4.9 EXPLORATORY ANALYSES

Plasma concentration-time of cortisol levels of all the volunteers will be quantified and tabulated in a csv file to explore the potential effects of kava on the plasma cortisol.

10 SUPPORTING DOCUMENTATION AND OPERATIONAL CONSIDERATIONS

10.1 REGULATORY, ETHICAL, AND STUDY OVERSIGHT CONSIDERATIONS

10.1.1 INFORMED CONSENT PROCESS

Protocol PAR-18-829

Informed consent is a process that is initiated prior to the individual agreeing to participate in the study and continues throughout study participation. Extensive discussion of risks and possible benefits of study participation will be provided to subjects and their families, if applicable. A consent form describing in detail the study procedures and risks will be given to the subject. Consent forms will be IRB-approved, and the subject is required to read and review the document or have the document read to him or her. The investigator or designee will explain the research study to the subject and answer any questions that may arise. The subject will sign the informed consent document prior to any studyrelated assessments or procedures. Subjects will be given the opportunity to discuss the study with their surrogates or think about it prior to agreeing to participate. They may withdraw consent at any time throughout the course of the study. A copy of the signed informed consent document will be given to subjects for their records. The rights and welfare of the subjects will be protected by emphasizing to them that the quality of their clinical care will not be adversely affected if they decline to participate in this study. The consent process will be documented in the clinical or research record. To complete the informed consent process at the end of study participation, study staff will inform the subject when his/her participation has come to an end and will document the discussion in the study record.

10.1.1.1 CONSENT/ASSENT AND OTHER INFORMATIONAL DOCUMENTS PROVIDED TO PARTICIPANTS

All consented subjects will be provided a copy of their fully executed informed consent document.

10.1.1.2 CONSENT PROCEDURES AND DOCUMENTATION

Each subject will review the informed consent document with the study coordinator and will be provided time to ask and receive answers to any questions. The name of the person obtaining consent will be documented along with date and time consent was obtained.

10.1.2 STUDY DISCONTINUATION AND CLOSURE

This study will be stopped prior to its completion if: (1) the intervention is associated with adverse effects that call into question the safety of the intervention; (2) difficulty in study recruitment or retention will significantly impact the ability to evaluate the study endpoints; (3) any new information becomes available during the trial that necessitates stopping the trial; or (4) other situations occur that might warrant stopping the trial."

If at any time during the study the participants are found to be at excessive risk, the study will be terminated. All key research personnel have completed the required human subjects training course. Key personnel include all individuals responsible for the design and conduct of the study.

10.1.3 CONFIDENTIALITY AND PRIVACY

Protocol PAR-18-829

Subject confidentiality is strictly held in trust by the investigators, study staff, and the sponsor(s) and their agents. This confidentiality is extended to cover testing of biological samples and genetic tests in addition to any study information relating to subjects.

The study protocol, documentation, data, and all other information generated will be held in strict confidence. No information concerning the study or the data will be released to any unauthorized third party without prior written approval of the sponsor.

The study monitor or other authorized representatives of the sponsor may inspect all study documents and records required to be maintained by the investigator, including but not limited to, medical records (office, clinic, or hospital) for the study subjects. The clinical study site will permit access to such records. All research material will be treated in a confidential manner, and only research staff will have access to the data. Confidentiality will be maintained by assigning identification numbers for all aspects of the project; all data entered into computer databases will use only this identifier. Data are kept in separate coded REDCap data sets and in locked cabinets in locked rooms at UF with access limited to a small number of study personnel. All clinical and other records have identifying names of participants and relatives removed. Electronic data will be password protected and stored in a database on a secure server that is also password protected, with no patient identifying information. No identifiable individual data are presented in scientific publications. Only research personnel will have access to this data.

10.1.6 SAFETY OVERSIGHT

The Data and Safety Monitoring Plan for this project will also include monitoring by an independent Data Safety Monitoring Board (DSMB), consisting of an anxiety disorders expert ([name]), a hepatologist ([name]), a statistician ([name]), and a pharmacologist ([name]). These individuals will have no affiliation to the proposed study. The DSMB will review any serious adverse event that is reported within 48 hours. They will also convene annually and at the end of the study to review all adverse events. Adverse events that are serious and unexpected will be immediately reported to the IRB, NIH, and FDA (if warranted). Non-serious unanticipated problems shall be described in annual reports to the IRB and NIH. The DSMB will review the adverse events and discuss any concerns regarding them with the Principal Investigators.

Study progress and safety will be reviewed monthly (and more frequently if needed). Progress reports, including patient recruitment, retention/attrition, and AEs will be provided to the Independent Monitor(s) semi-annually. An Annual Report will be compiled and will include a list and summary of AEs. In addition, the Annual Report will address (1) whether AE rates are consistent with pre-study assumptions; (2) reason for dropouts from the study; (3) whether all participants met entry criteria; (4) whether continuation of the study is justified on the basis that additional data are needed to accomplish the stated aims of the study; and (5) conditions whereby the study might be terminated prematurely. The Annual Report will be sent to the Independent Monitor(s) and will be forwarded to the IRB and NCCIH, FDA, and sponsoring industry collaborator. The IRB and other applicable recipients will review progress of this study on an annual basis

10.1.7 CLINICAL MONITORING

Protocol PAR-18-829

The study team will generate Study Reports for the Independent Monitor and will provide information on the following study parameters: liver function, serious adverse events, and pharmacokinetic data.

Study Report tables will be generated only from aggregate (not by group assignment) baseline and aggregate safety data for the study population.

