The study coordinator for the proposed project has 6 years of experience and will be trained in all study procedures. She will coordinate the screening of potential participants and will meet with [name] weekly to discuss study progress. [name], a gastroenterologist with expertise in hepatology and liver transplantation, will be responsible for overseeing the medical safety monitoring for this trial. He has extensive experience as a medical monitor for national clinical trials of multiple medications. He will communicate with [name] on a regular basis, and will also communicate any and all adverse events to the data safety monitoring board. He will interpret the results of the liver biochemistries (all results will be blinded to treatment condition) and will be responsible for referring participants to appropriate additional clinical evaluation and intervention if needed.

Effective screening will rule out active medical or psychiatric conditions, including supplement or medication use, chronic alcohol use, and evidence of pre-existing liver disease that may prevent someone from participating in the studies. Once the subject enters the study, an experienced research team will closely follow him or her. The research team has developed considerable expertise in monitoring the safety of subjects participating in research studies. An experienced research psychiatrist and the hepatologist is available 24 hours a day, 7 days a week. If at any point in the procedures

Protocol PAR-18-829 11 May 2021

symptoms become distressing or dangerous, subjects will be withdrawn from the study and, if necessary, treatment instituted.

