4 STUDY DESIGN

4.1 OVERALL DESIGN

- To develop a pharmacokinetic model to identify the best dose and dosage regimens of flavokavain A/B free kava for its further development as a drug for the treatment of GAD
- Phase 1 Single site study
- Open-label
- An equal number of male and female subjects will be enrolled in study. All races and ethnicities will be included. A dose of supplement kava 225 mg will be administered at baseline either in a single dose or dosed at three times during the study visit. Study group-Pharmacokinetics is a single day intervention with 12 week follow up post study drug ingestion. Ten subjects will be recruited and enrolled into the pilot pharmacokinetic study. Each subject will stay in the out-patient Clinical Research Center (CRC) at the CTSI during the 12 hour study period. Participants will be asked to refrain from food, liquids other than water, and medications for 12 hours prior to entering the Clinical Research Center of the UF CTSI. They will have an indwelling venous catheter placed in the lower arm to facilitate the multiple blood collections during the study. Each subject will take three 75 mg kava capsules and ten blood draws (2 mL EDTA vacutainer) will be collected corresponding to the absorption, distribution, metabolism and excretion phase of the pharmacokinetic curve. Specifically, blood will be withdrawn at baseline and 0.5, 1, 2, 3, 4, 5, 6, 8 and 12 hours after kava ingestion. The blood samples will be processed and then stored at -80°C till analysis. The period of follow up for any delayed adverse effects (e.g., monitoring of liver function) will be extended such that all participants will be followed for a full 12 weeks after their last kava ingestion. CYP2D6 testing will be conducted to determine if the genotype affects the pharmacokinetics of kava.

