6.2 PREPARATION/HANDLING/STORAGE/ACCOUNTABILITY

6.2.1 ACQUISITION AND ACCOUNTABILITY

Subjects will be provided with either a onetime dosage or a three time dose of kava (each capsule being 75mgs for a total of 225 mgs for a daily total dose) at the baseline visit. Ingestion of kava will be monitored by the research coordinator and documented on a study drug accountability log.

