6.3 MEASURES TO MINIMIZE BIAS: RANDOMIZATION AND BLINDING

There is no randomization process in this study. All qualified and consented study participants will receive the same total daily dose of kava and will follow through will all follow up procedures.

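### Monitor tables pooled across regimens, and liver results read blind to treatment, protect no blind in this open-label study and leave no stated route by which the monitor sees safety data by regimen

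*Combined protocol and SAP*

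**What the plan says.** **The reports.** Section 10.1.7 has the study team give the Independent Monitor "information on the following study parameters: liver function, serious adverse events, and pharmacokinetic data". It then restricts the tables: "Study Report tables will be generated only from aggregate (not by group assignment) baseline and aggregate safety data for the study population". The restriction names baseline and safety data. It does not say that pharmacokinetic data are pooled.

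**The liver results.** Section 2.3.3 has the medical monitor interpret the liver biochemistries and adds that "all results will be blinded to treatment condition".

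**The design.** Section 4.1 describes an open-label study: "Ten subjects will be recruited and enrolled into the pilot pharmacokinetic study". The dose is given "either in a single dose or dosed at three times during the study visit", and Section 6.2.1 likewise provides for "either a onetime dosage or a three time dose of kava". Section 6.3 states that there is no randomization and that "All qualified and consented study participants will receive the same total daily dose of kava". The current sections give no rule for who receives which regimen. Only the amendment history in 10.4 mentions one: the first five participants on the single dose, the second five on three doses.

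**Other safety routes.**
- Section 9.4.4 has the medical monitor notified of elevated liver enzymes. Its examples are values above 3 × ULN on two repeated measures, or above 5 × ULN once.
- Section 8.3.1 lets an abnormal laboratory value count as an adverse event.
- Section 2.3.3 has the medical monitor pass all adverse events to the DSMB.
- Section 10.1.6 has the DSMB review reported SAEs within 48 hours and all adverse events annually and at study end. It also sends the Independent Monitor(s) an Annual Report that lists adverse events.

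**The concern.** Pooling across groups and masking treatment are safeguards for a blinded comparison, and this study has neither a blind nor a randomized comparison. What it has is two ways of giving the same total dose, and Section 4.1 makes the choice of a dosing regimen a purpose of the study. Whether a liver rise or another event clusters in one regimen is therefore a natural question for the independent monitor. The tables prescribed for that monitor cannot answer it.

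Liver injury is also the main risk discussed in Section 2.3, and in ten people a signal may be one person. It matters whether that person's values reach the monitor as individual values, and with the regimen attached.

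**Working it through.** The plan states no figure to reproduce here. The check compares the safety routes and then illustrates what pooling does.

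**1. Which routes show the person, and which show the regimen?**

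| Route | Individual shown? | Regimen said to be shown? |
|---|---|---|
| Study Report tables (10.1.7) | No: aggregate | No: expressly not by group |
| Medical monitor's reading of liver results (2.3.3) | Yes | No: blinded to treatment condition |
| Notification of elevated enzymes (9.4.4) | Yes, to the medical monitor and the participant | Not stated |
| Adverse events passed to the DSMB (2.3.3, with 8.3.1) | Yes, if recorded as an AE | Not stated |
| SAE review and Annual Report AE list (10.1.6) | Yes, for SAEs and listed AEs | Not stated |

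No row says that regimen is shown.

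**2. What pooling does to a regimen pattern.** Assume five per regimen, as in the amendment history. A pooled count of 3/10 fits four splits: 3+0, 2+1, 1+2 and 0+3. The tables cannot tell them apart. Two-sided Fisher exact p-values show how little a formal test would add:
- 3/5 vs 0/5: 2 × C(5,3)/C(10,3) = 2 × 10/120 = 0.167
- 4/5 vs 0/5: 2 × C(5,4)/C(10,4) = 2 × 5/210 = 0.048
- 5/5 vs 0/5: 2 × 1/C(10,5) = 2/252 = 0.008

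With no events in the other regimen, it takes at least 4/5 to reach p < 0.05. The loss is therefore descriptive.

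**3. Which individual values lack a route to the independent monitor?** Set against the 9.4.4 examples:
- above 5 × ULN once: goes to the medical monitor;
- above 3 × ULN on two repeated measures: goes to the medical monitor;
- between 3 and 5 × ULN once, not repeated: meets neither example. The medical monitor may still see it when interpreting the results under 2.3.3, but it is sent on to the DSMB or the independent monitor only if it is recorded as an adverse event.

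**4. What a pooled mean would show.** The plan does not say whether the tables give means, counts or ranges. If they give means, then mean = (peak + (n − 1) × level of the others)/n. The level of the others is not in the documents; it is assumed to be 0.3, 0.5 or 0.8 × ULN.

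| One person at | Others at | Mean of all 10 | Mean of that regimen's 5 |
|---|---|---|---|
| 5 × ULN | 0.3 | (5 + 2.7)/10 = 0.77 | (5 + 1.2)/5 = 1.24 |
| 5 × ULN | 0.5 | (5 + 4.5)/10 = 0.95 | (5 + 2.0)/5 = 1.40 |
| 5 × ULN | 0.8 | (5 + 7.2)/10 = 1.22 | (5 + 3.2)/5 = 1.64 |
| 3 × ULN | 0.3 | (3 + 2.7)/10 = 0.57 | (3 + 1.2)/5 = 0.84 |
| 3 × ULN | 0.5 | (3 + 4.5)/10 = 0.75 | (3 + 2.0)/5 = 1.00 |
| 3 × ULN | 0.8 | (3 + 7.2)/10 = 1.02 | (3 + 3.2)/5 = 1.24 |

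If the tables give counts, the same person appears as 1/10. If they give a range, that person is the maximum. The last column shows that splitting means by regimen would still dilute one case, whereas a per-participant listing would not.

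**The case against.** A reader might infer that one liver elevation would be averaged away and that the monitor could not do its job. The documents do not support this. A hepatology specialist interprets the biochemistries, the 9.4.4 trigger works person by person, abnormal laboratory values can be adverse events, and adverse events go to a DSMB that includes a hepatologist. The 10.1.7 restriction covers Study Report tables and does not forbid the AE list that 10.1.6 provides. No section says that the tables report means, and a value above 5 × ULN is one that the plan already catches. Section 9.4.4 also gives its thresholds as examples, so staff could notify lower values.

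It can also be said that regimen matters little when everyone takes the same total dose on one day, that five against five supports no useful test, and that the blinding phrase has little to act on in an open-label study.

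Most of this stands, and it limits the point to the Study Report tables and to regimen. It does not remove the point. None of these routes is said to carry regimen. Notifying a single value of 3 to 5 × ULN is possible but not required. A written rule that hides group in an open-label study still contradicts the design, even if it has little effect in practice.

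**Conclusion.** The point holds in a limited form. The pooling rule in 10.1.7 and the blinding phrase in 2.3.3 do not fit an open-label, non-randomized study, and no safety route is said to show regimen. The main consequence is descriptive: a split such as 3/5 against 0/5 would appear as 3/10. This rests on five per regimen, which stands only in the amendment history.

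The individual-level gap is confined to a single, unrepeated value of 3 to 5 × ULN that is not recorded as an adverse event. Dilution to a pooled mean of about 0.8 to 1.2 × ULN for one person at 5 × ULN is conditional twice over: on the tables showing means, and on the others lying at 0.3 to 0.8 × ULN.

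A reader might also take the empty entry under 8.3.8 to mean that a liver elevation gets no separate attention. It does not mean that, because 9.4.4 handles elevations separately. The point concerns oversight reporting and does not touch the primary half-life endpoint.

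**What to change.** Replace the restricting sentence in 10.1.7 so that each Study Report contains:
- a per-participant listing of ALT, AST, ALP and bilirubin as multiples of ULN, by visit, with regimen shown;
- AE and SAE listings by participant, with regimen shown.

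Pooled summaries can stay beside these listings. Reconcile the blinding wording in 2.3.3 with the open-label design in 4.1. No change to the 9.4.4 thresholds or to any clinical rule is needed.

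The cost is a listing of ten participants and a few lines of text. The liver values are already scheduled, and 6.2.1 already has kava ingestion documented on an accountability log, so no new data are needed.
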